11. CHANGES TO THE STATISTICAL METHODOLOGY PRESENTED IN THE PROTOCOL

Table 11: Changes from the Statistical Analysis Plan That Was Presented for the Second Interim CSR

Protocol Section/Existing Contents	SAP Section/Revision Text	Reason for Change
7.1; 7.2; 7.3 Objectives and Purpose	3.1; 3.2; 3.3 The bulleted items in the objectives were revised for accuracy and clarity.	For clarification
12.4.1 Intent-to-Treat Population: includes all enrolled subjects. Other populations may be defined in the SAP.	6.1.1; 6.1.3; 6.1.4 The SAP uses 'All Enrolled Subjects' population, but no ITT population. The SAP also includes Efficacy and PK populations.	(1) For clarity (2) There may be improper usage of the term ITT analyses, as the study was not randomized.
12.4.4.2; 12.4.4.5 Analyses are organized for: (1) Individual Cohorts, and overall; (2) Combined Cohorts 1, 3, and 4 (for ambulatory subjects); and (3) Combined Cohorts 1 and 4 (for ERT-experienced subjects)	General The SAP is organized as one document with three sub-studies based on the different stages in the study design (Stage 1, Stage 2, and Stages 3 and 4). However, the presentation of results for Stages 3 and 4 is consistent with the way analyses are organized in the protocol.	Organization of SAP is designed to meet the needs of the interim CSR.
12.4.4.2; 12.4.4.3 Summary statistics specified are: n, mean, SD, median, minimum, and maximum.	6.2 The first quartile (Q1) and third quartile (Q3) have been added to the summary statistics.	Q1 and Q3 can help in understanding the data distribution.
12.4.4.3 Safety Analyses	10.1; 10.3 Additional details have been provided for the safety analyses so as to align them to the ongoing pivotal Study ATB200-03.	For clarification and consistency
12.4.4.3 – Safety Analyses Shift changes and shift tables are described for vital signs, clinical labs, ECG based on PCS values in Protocol Appendix 2.	10.4; 10.5; 10.6 No more shift tables. Shift changes are now based on the use of PDLC. Although the PDLC criteria are similar to the PCS, they are not exactly the same.	To keep some level of consistency with Study ATB200-03.

Abbreviations: CSR = clinical study report; ECG = electrocardiogram; ERT = enzyme replacement therapy; ITT = intent-to-treat; PCS = potentially clinically significant; PDLC = pre-defined limits of change; PK = pharmacokinetic; SAP = statistical analysis plan; SD = standard deviation

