Details of the analysis methods related to all non-PK-specific parameters will be provided in a separate SAP for the study.

In general, descriptive statistics (n, mean, standard deviation [SD], median, minimum, and maximum) will be provided for all efficacy continuous variables. Each cohort will have its own baseline, and analysis will be performed by cohort and overall. In addition, summary analyses will be performed by combining Cohort 1, 3, and 4 for ambulatory subjects, or by combining Cohort 1 and 4 for ERT-experienced subjects. For Cohort 1, the analysis will also be provided by treatment dosing regimen. The visit values and the change (and percent change) from baseline to the post-baseline assessment will be analyzed by scheduled visit. The 95% confidence interval for the mean (and percent mean) change from baseline by scheduled visit will be provided for summary purposes only. In addition, the visit values and derived values for each subject will be provided in data listings.

Safety and other variables that are continuous (including vital signs, laboratory assessments, and immunogenicity values) will similarly be analyzed using descriptive statistics. Shift tables will be generated for safety laboratory parameters.

Summary statistics will be provided for all variables that are not PK parameters.

Adverse events and other variables that are categorical will be summarized using counts and percentage. In addition, categorical variables (excluding AEs) will be summarized by scheduled visits.

Interim Analyses: Interim analyses will be performed during the study as needed. Details for the interim analysis will be included in the SAP.

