Distribution: Miglustat does not bind to plasma proteins. Mean apparent volume of distribution of miglustat is 83 to 105 liters in Gaucher patients. At steady state, the concentration of miglustat in cerebrospinal fluid of six non-Gaucher patients was 31.4% to 67.2% of that in plasma, indicating that miglustat crosses the blood brain barrier (Zavesca Labeling-Package Insert 2014).

Metabolism and Excretion: The major route of excretion of miglustat is via kidney. Following administration of a single dose of 100 mg ^{14}C -miglustat to healthy volunteers, 83% of the radioactivity was recovered in urine and 12% in feces. In healthy subjects, 67% of the administered dose was excreted unchanged in urine over 72 hours. The most abundant metabolite in urine was miglustat glucuronide accounting for 5% of the dose. The terminal half-life ($t_{1/2}$) of radioactivity in plasma was 150 hours, suggesting the presence of one or more metabolites with a

prolonged half-life. The metabolite accounting for this observation has not been identified, but may accumulate and reach concentrations exceeding those of miglustat at steady state. Miglustat did not inhibit or induce substrates of cytochrome P450 enzymes (Zavesca Labeling-Package Insert 2014).

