12.2. Hypotheses

No formal statistical hypotheses are specified for this study.

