12.4.4.3. Safety Analyses

Adverse events and concomitant medications terms will be coded using Medical Dictionary for Regulatory Activities (MedDRA) version 16.1 or higher and WHO Drug Dictionary.

In general, TEAEs will be grouped by MedDRA System Organ Classes and by Preferred Terms. Summary statistics will be provided by cohort for AEs, ECG shift changes, vital signs shift changes, and clinical laboratory shift data based on the potentially CS values defined in

Appendix 2. In addition, summary statistics (n, mean, median, SD, minimum, and maximum) will be provided for values at each visit and changes from baseline at each visit for ECG, vital signs, and clinical laboratory assessments by cohort.

Prior and concomitant medications will also be summarized by cohort. A by-subject listing of protocol deviations will be provided.

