APPENDIX 2. POTENTIALLY CLINICALLY SIGNIFICANT GUIDELINES

Criteria for identifying abnormalities as potentially CS are based on the Guidelines for the Division of Neuropharmacological Drug Products, US Food and Drug Administration (revised on April 2, 1987). The laboratory values identified below are not inclusive of all the safety laboratory analytes that will be assessed during this clinical trial. Safety laboratory analytes which are known to be elevated in some adults with Pompe disease (eg, AST, ALT, LDH) and safety laboratory analytes which are not listed below will be reviewed to determine if they are to be noted as potentially CS based on the magnitude of the out of range value as compared to the normal range and the subject's baseline value, and whether the out of range value is coded as CS by the principal investigator.

Laboratory Values		
Variable	Criterion Values	
	Standard Units	SI Units
Chemistry		
SGOT (AST)	$\geq 3 \times$ Upper Limit Normal	
SGPT (ALT)	$\geq 3 \times$ Upper Limit Normal	
Alkaline Phosphatase	$\geq 3 \times$ Upper Limit Normal	
LDH	$\geq 3 \times$ Upper Limit Normal	
BUN	≥ 30 mg/dL	≥ 10.7 μ M
Creatinine	≥ 2.0 mg/dL	≥ 176.8 μ M
Uric Acid	Male ≥ 10.5 mg/dL	≥ 624.6 μ M
	Female ≥ 8.5 mg/dL	≥ 505.6 μ M
Bilirubin (Total)	≥ 2.0 mg/dL	≥ 34.2 μ M
Hematology		
Hematocrit	Male $\leq 37\%$	
	Female $\leq 32\%$	
Hemoglobin	Male ≤ 11.5 g/dL	
	Female ≤ 9.5 g/dL	
Platelets	$\leq 75,000/\text{mm}^3$ or $\geq 700,000/\text{mm}^3$	$\leq 75 \times 10^9/\text{L}$ or $\geq 700 \times 10^9/\text{L}$
Leukocytes	$\leq 2,800/\text{mm}^3$ or $\geq 16,000/\text{mm}^3$	$\leq 2.8 \times 10^9/\text{L}$ or $\geq 16 \times 10^9/\text{L}$
Eosinophils	$\geq 10\%$	
Neutrophils	$\leq 15\%$	
Urinalysis		
Protein	Increase of ≥ 2 units	
Glucose	Increase of ≥ 2 units	
Casts	Increase of ≥ 2 units	

Abbreviations: BUN = blood urea nitrogen; LDH = Lactate dehydrogenase; SGOT (AST) = serum glutamic oxaloacetic transaminase (aspartate aminotransferase); SGPT (ALT) = serum glutamic pyruvic transaminase (alanine aminotransferase)

Vital Sign Values			
Variable	Criteria		Change Relative to Baseline
Heart Rate	≥ 120 bpm	and an	increase of ≥ 15 bpm
	≤ 50 bpm	and a	decrease of ≥ 15 bpm
Systolic Blood Pressure	≥ 180 mmHg	and an	increase of ≥ 20 mmHg
	≤ 90 mmHg	and a	decrease of ≥ 20 mmHg
Diastolic Blood Pressure	≥ 105 mmHg	and an	increase of ≥ 15 mmHg
	≤ 50 mmHg	and a	decrease of ≥ 15 mmHg
Weight			change of $\geq 7\%$ body weight

ECG Values		
ECG parameter	Low	High

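### SAP Table 8 omits 10 of the 17 laboratory analytes that have protocol limits, so no count of subjects crossing those limits is planned, and Table 11 does not name them

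*SAP*

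**What the plan says.** The Protocol Synopsis states: "Shift tables will be generated for safety laboratory parameters". Protocol Section 12.4.4.3 gives the basis, promising by-cohort summaries of "clinical laboratory shift data based on the potentially CS values defined in" Appendix 2. That appendix sets limits for 17 chemistry, hematology and urinalysis items.

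SAP Section 11 (Table 11) reverses this: "No more shift tables. Shift changes are now based on the use of PDLC". On how the two sets compare, it says: "Although the PDLC criteria are similar to the PCS, they are not exactly the same". The reason given is: "To keep some level of consistency with Study ATB200-03". SAP Section 2 states that its analyses supersede those in the protocol.

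Under SAP Section 10.4, the percentage of subjects meeting a Table 8 criterion is summarised over the whole period from the first dose in Stage 2 Period 5, with unscheduled visits included. A subject is listed if any post-baseline value meets a criterion. Section 10.8 adds a combined listing that is also triggered by these limits. Separately, Section 10.4 gives quantitative laboratory results the Section 6.2.1 statistics (n, mean, SD, median, quartiles, minimum, maximum) for value, change and percent change. It also flags out-of-range values in full listings.

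**The concern.** Change from baseline in safety laboratory values is a primary endpoint (Protocol Section 12.1.1). Cohorts are planned at 4 to 12 subjects, so the safety reading rests largely on individuals. The protocol had already chosen thresholds for identifying them. The SAP drops those thresholds for most of the listed analytes and gives layout consistency as the only reason.

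The kidney and blood markers are ones a reader would expect to see. Protocol Section 6.2 states: "The major route of excretion of miglustat is via kidney". Section 8.5 includes the renal and the blood and lymphatic organ classes among those that define stopping events.

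At stake is whether a reader of the final report can see how many subjects passed the protocol's creatinine limit, or fell to its leukocyte limit, without working through every line of the laboratory listings.

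**Working it through.** No power, alpha or effect size enters here: "No formal statistical hypotheses are specified for this study". The check compares two lists and then asks which outputs remain.

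**Step 1. Compare Protocol Appendix 2 with SAP Table 8.**

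| Group | Items | Count |
|---|---|---|
| In both | AST, ALT, uric acid, total bilirubin, hemoglobin, platelets, eosinophils | 7 |
| Appendix 2 only, blood | creatinine, BUN, ALP, LDH, hematocrit, leukocytes, neutrophils | 7 |
| Appendix 2 only, urine | protein, glucose, casts | 3 |
| Table 8 only | albumin, bicarbonate, calcium, phosphorus, potassium, sodium, CK, and two transaminase-with-bilirubin composites | 9 |

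Appendix 2 has 7 + 7 + 3 = 17 items and Table 8 has 7 + 9 = 16 entries. The omitted items number 17 − 7 = 10. SAP Table 7 lists all seven omitted blood analytes as collected (leukocytes as WBC count).

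**Step 2. See what remains for the omitted items.**

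- The incidence summary and subject listing in Section 10.4, and the laboratory part of the Section 10.8 listing, all depend on Table 8. None can contain an omitted analyte.
- The seven blood analytes keep by-visit statistics, including minimum and maximum, and the out-of-range flag in the listings.
- Categorical urinalysis findings go to listings only.
- Protocol Section 10.2.11 requires clinically significant laboratory results to be reported as adverse events. These are then counted by system organ class and preferred term.

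**Step 3. Ask whether the by-visit extremes would show one abnormal subject.** Take a hypothetical creatinine rise from 80 to 180 micromol/L in one of n subjects, with the others unchanged. These values are assumed; the protocol limit is 176.8.

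- Shift in the mean = (180 − 80)/n. This is 100/4 = 25 for n = 4, 100/10 = 10 for n = 10, and 100/12 = 8.3 for n = 12.
- Maximum change in the same table = at least 100, and maximum value = at least 180.

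The mean hides the case but the maximum shows it, provided the value is the one kept for that window.

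**Step 4. Check which value is kept.** SAP Section 6.6 keeps the value closest to the target day. In Stage 4, the Month 30 window is Day 812 to 991 for Cohorts 2 to 4 (991 − 812 + 1 = 180 days). For Cohort 1 it is Day 854 to 1033 on the re-scaled clock (1033 − 854 + 1 = 180 days). Assume the scheduled visit falls within 7 days of the target. Any value more than 7 days away then loses to it, which covers 180 − (2 × 7 + 1) = 165 of the 180 days. An unscheduled peak on one of those days reaches the listing but not the by-visit minimum or maximum. The PDLC summary would have captured it, because it takes all visits over the whole period.

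**Step 5. Check units before reusing the limits.**

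- Creatinine: 2.0 × 10,000/113.12 = 176.8 micromol/L, which agrees with Appendix 2.
- BUN: 30 × 10/28.014 = 10.7 mmol/L, but Appendix 2 prints 10.7 micromolar.
- Uric acid (already in Table 8): 10.5 × 10,000/168.11 = 624.6 and 8.5 × 10,000/168.11 = 505.6 micromol/L, but Table 8 prints both in mM, 1,000 times too high.

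**The case against.** The strongest reply is that little is lost. The study is descriptive. In cohorts this small the by-visit maximum is one person's value, every out-of-range result is flagged, and a value judged clinically significant is counted as an adverse event. The protocol left details to the SAP, and the SAP discloses the change. Table 8 also adds nine entries that Appendix 2 lacks, so this is an exchange rather than a pure removal. Hemoglobin, kept with four criteria, largely covers hematocrit. Appendix 2 itself names LDH among analytes raised in some adults with Pompe disease.

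Most of this stands, and it rules out three stronger readings that a reader might infer:

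- **The omitted blood analytes are left with means and listings only.** Section 6.2.1 supplies quartiles and extremes, and Step 3 shows that the extremes would normally reveal a marked rise.
- **White-cell abnormalities lose all threshold reporting.** Table 8 keeps eosinophils above 10%; only total leukocytes and neutrophils drop out.
- **Renal excretion of miglustat implies expected renal harm.** Excretion concerns clearance. Protocol Section 6.4.1 reports no adverse treatment-related chemistry findings, and no treatment-related organ-weight or microscopic findings.

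The reply does not supply a count against a fixed limit. The adverse event route depends on investigator judgement, and the by-visit extremes depend on which value wins the window. The disclosure does not tell a reader which analytes were dropped. The LDH argument also applies to AST and ALT, which Appendix 2 names alongside it and Table 8 keeps.

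**Conclusion.** The point holds as a reporting gap of modest size. Ten of 17 protocol-defined laboratory limits, seven of them for blood analytes, have no limit-based count or percentage of subjects and no entry to the PDLC listings, and Table 11 does not identify them. Individual abnormalities remain traceable, so safety signals are not concealed. They are harder to find, and an unscheduled peak is the case most likely to be missed in the tables. The change is worth making because it restores the protocol's own thresholds for a primary safety endpoint from data already collected.

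This rests on reading Table 8 as the complete list of laboratory PDLC criteria. It applies to outputs from Stage 2 Period 5 onward. The documents do not say which limits were used in the first interim report, from which Stage 1 and 2 results will be carried over.

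**What to change.** Before database lock, add rows to SAP Table 8 at the Appendix 2 limits, used for reporting only:

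- **At least:** creatinine ≥ 2.0 mg/dL (176.8 micromol/L); BUN ≥ 30 mg/dL (10.7 mmol/L, correcting the printed micromolar unit); ALP ≥ 3 × ULN; leukocytes ≤ 2.8 or ≥ 16 × 10⁹/L; neutrophils ≤ 15%.
- **Preferably also:** LDH ≥ 3 × ULN; hematocrit ≤ 37% (male) or ≤ 32% (female).
- **For anything still left out, including the three urinalysis items:** name it in Table 11 with a reason.

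A baseline-to-worst shift table for the omitted analytes would also serve. While Table 8 is open, correct the uric acid unit to micromolar.

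The cost is a few table rows and a small layout difference from Study ATB200-03. No new data are needed.

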12. GENERAL PROGRAMMING INFORMATION

12.1. General

All programmed table, figure, and listing outputs, unless specified otherwise, will be generated using the SAS version 9.4 or later. The programmed outputs will be similar to the format/appearance of the table and listing shells. However, space/formatting limitations may dictate changes in the programmed output. The footnotes specified in the table and listing shells may be changed as necessary for clarifying table entries or the explanation of algorithms or methods used for producing the entries. Significant changes in footnotes will be discussed prior to their implementation.

12.2. Format of Tables/Listings

Tables and listings should be produced in landscape mode and centered horizontally. Required margins are 1 inch for the top, left, right, and bottom margins. All outputs should have a 3-line header at the upper left margin:

Amicus Therapeutics
Protocol ATB200-02
Confidential

Other important formats for the tables and listings include the following:

- All outputs should have a 1-line footer with explanatory notes that include the date of data extraction, SAS program name including the path that generates the output, and the date and time the output was produced at the lower left margin of the footer. Tables will have the report listings for the data analyses presented in the table identified at the lower left margin, and listings will have the source eCRF identified.
- Tables and listings should be internally paginated in relation to the total length for that table or listing (ie, Page n of N, where n is the page number within the table or listing, and N is the total number of pages for that table or listing).
- The table, figure, and listing numbering will be based on the ICH Guideline E3. A number should identify each table/listing, and the table designation (eg, Table 1) should be centered above the title. A decimal system (eg, x, x.y, x.y.z) should be used to identify tables/listings with related contents. The title should be centered and in mixed-case characters.
- The title and table/listing designation should be single-spaced but are separated from the content of the table/listing by a space and a solid underline. The study population and/or subgroup (eg, Safety population) should be identified on the line immediately following the title.
- Column headings should be in initial upper-case characters. For numeric variables, the unit should be included in the column heading when appropriate.

- Footnotes should be single-spaced but separated by an underline and a space from the text of the table/listing. The notes should be aligned vertically by the left vertical border of the table/listing. Numeric references, which can be confused with data, should not be used; asterisks and other non-numeric symbols should be used to refer to footnotes.
- The dictionary (eg, MedDRA, WHO-DRUG) and the dictionary version numbers should be identified in the footnotes to the tables/listings for data coded with a dictionary. The source of the information (eg, Printed on CRF) should be identified if the data were not coded using a dictionary.
- For summarizations of categorical data, an Unknown or Missing category should be added to any variable for which information is not available for all subjects. However, only the number of unknown or missing subjects will be presented, and percent will be based on non-missing data.
- Individual data listings will be sorted and presented by treatment group, patient number, and visit date.

12.3. Data Formats

Unless otherwise specified, means and medians will be rounded and presented to 1 decimal place more than the raw (or actual measured) data and standard deviations to 2 decimal places more than the raw data. Minimum and maximum values will be presented to the same number of decimal places as the raw data.

Data in columns will be formatted as follows:

- Alphanumeric values will be center-aligned (in mixed upper and lowercase).
- Numerical data will be decimally aligned.
- Fractional data should be presented with the zero to the left of the decimal point (eg, 0.54).

Unless otherwise specified, percentages should be presented to 1 decimal place. Less than signs (ie, '<') should be presented as appropriate (eg, 0.04% should be presented as < 0.1%, not 0.0%).

Dates will be presented in DDMONYYYY format. Dates with partial missing data will be presented with a dash (ie, '-') for the missing data (eg, --JAN2005).

APPENDIX 1. DESCRIPTIONS AND DERIVATIONS OF EFFICACY ENDPOINTS

1. Pulmonary function tests (PFTs):

- Sitting forced vital capacity (FVC): maximum FVC (L) and percent predicted FVC (%)
- Supine forced vital capacity: maximum FVC (L) and percent predicted FVC (%)
- Maximum inspiratory pressure (MIP) (cm of water [cm H₂O])
- Maximum expiratory pressure (MEP) (cm of water [cm H₂O])
- Sniff nasal inspiratory pressure (SNIP) (cm of water [cm H₂O])
- The percent predicted values of MIP, MEP, and SNIP will be calculated as:
$$\% \text{ predicted} = (\text{actual result} / \text{predicted result}) * 100.$$

The predicted results are obtained using the following reference equations: [Uldry and Fitting, 1995](#) for MIP, MEP, and the lower limit of normal (LLN), and [Evans and Whitelaw, 2009](#) for the SNIP values.

Table 12: Predicted Equations for MIP, MEP, and SNIP

PFT	Male	Female
MIP	$120 - (0.41 \times \text{Age in years})$	$108 - (0.61 \times \text{Age in years})$
MIP LLN	$62 - (0.15 \times \text{Age in years})$	$62 - (0.50 \times \text{Age in years})$
MEP	$174 - (0.83 \times \text{Age in years})$	$131 - (0.86 \times \text{Age in years})$
MEP LLN	$117 - (0.83 \times \text{Age in years})$	$95 - (0.57 \times \text{Age in years})$
SNIP	$126.8 - (0.42 \times \text{Age in years})$	$94.9 - (0.22 \times \text{Age in years})$

Abbreviations: LLN = lower limit of normal; MEP = maximum expiratory pressure; MIP = maximum inspiratory pressure; PFT = pulmonary function test; SNIP = sniff nasal inspiratory pressure

2. Manual muscle testing (MMT):

- Right/left shoulder adduction
- Right/left shoulder abduction
- Right/left elbow flexion
- Right/left elbow extension
- Right/left hip flexion – ambulatory patients only
- Right/left hip abduction – ambulatory patients only
- Right/left hip adduction – ambulatory patients only
- Right/left knee flexion – ambulatory patients only
- Right/left knee extension – ambulatory patients only

Each manual muscle testing is evaluated on a scoring scale from 0 to 5: 0 = no muscle movement; 1 = visible muscle movement, but no movement at the joint; 2 = movement at the joint, but not against gravity; 3 = movement against gravity, but not against added resistance; 4 = movement against resistance, but less than normal; 5 = normal strength.

- Upper body muscle groups include right/left shoulder abduction, right/left shoulder adduction, right/left elbow flexion, and right/left elbow extension with the total score ranging from 0 – 40, based on these 8 muscle groups. That is,
Upper = Shoulder + Elbow.
- Lower body muscle groups include right/left hip flexion, right/left hip abduction, right/left hip adduction, right/left knee flexion, and right/left knee extension with the total score ranging from 0 – 50, based on these 10 muscle groups. That is,
Lower = Hip + Knee.
- Proximal body muscle groups include right/left hip flexion, right/left hip abduction, right/left hip adduction, right/left shoulder abduction, and right/left shoulder adduction with the total score ranging from 0 – 50, based on these 10 muscle groups. That is, Proximal = Shoulder + Hip.
- Total MMT score ranges from 0 – 90 based on all 18 muscle groups, and it will be analyzed as a continuous variable. Higher scores indicate less disease impact on muscle functions. That is, Total = Upper + Lower.

Note: If there are many instances of missing testing scores (ie, if $\geq 50\%$ of the testing scores [at least 9 out of 18] are missing), then the total will be normalized to 100%. That is, the total score will be prorated as: Total = (Mean of all available scores) $\times 18$.

Note: The right/left hip adduction muscle group was added later in the study, and so it will not appear in MMT summaries provided at earlier time points in Stage 3. For example, the lower body score at the earlier time points will range from 0 – 40 (based on 8 muscle groups) and the total MMT score at the earlier time points will range from 0 to 80 (based on 16 muscle groups).

Ambulatory subjects were expected to perform all the muscle tests for both lower and upper body, while non-ambulatory subjects were to perform the muscle tests for only upper body.

- Body parts are shoulder, elbow, knee, and hip.

Note: Each body part is the sum of its corresponding 4 muscle groups,
eg, shoulder = right/left shoulder abduction + right/left shoulder adduction.

3. Quantitative muscle tests (QMTs) using hand-held dynamometer (in kg):

- Right/left shoulder adduction
- Right/left shoulder abduction
- Right/left elbow flexion
- Right/left elbow extension
- Right/left hip flexion – ambulatory patients only

- Right/left hip adduction – ambulatory patients only
- Right/left hip abduction – ambulatory patients only
- Right/left knee flexion – ambulatory patients only
- Right/left knee extension – ambulatory patients only

Note: The muscle tests involving the upper body, lower body, total, and the proximal body (made up of the 5 moves from shoulder + hip) will be summarized.

4. Six-minute walk distance (6MWD) is the distance in meters (m) walked in the 6-minute walk test. It was performed by only ambulatory subjects.
 - Percent predicted 6MWD is calculated as:
$$\% \text{ predicted 6MWD} = (\text{actual 6MWD} / \text{predicted 6MWD}) * 100$$
(rounded up or down based on standard rounding rules), where the predicted values are derived for males and females using Enright equations ([Enright and Sherill, 1998](#)) as follows:
Males: $6\text{MWD} = (7.57 \times \text{Height in cm}) - (5.02 \times \text{Age in years}) - (1.76 \times \text{Weight in kg}) - 309 \text{ m}$
Females: $6\text{MWD} = (2.11 \times \text{Height in cm}) - (5.78 \times \text{Age in years}) - (2.29 \times \text{Weight in kg}) + 667 \text{ m}$
Height is measured at the Screening visit. Weight is weight at same date that the 6MWD was measured. If weight was not measured at that date, then the weight measurement closest to the given date will be used. Age is the age at the 6MWD assessment, and it is calculated as: $\text{FLOOR}([\text{age at assessment} - \text{birthdate}] / 365.25)$.
5. Gait, Stairs, Gowers', Chair (GSGC) total score is obtained by adding up the scores attributed to each of the following 4 functional tests:
 - Gait test is based on the 10-meter walk test (10MWT). This is scored as: 1 = normal; 2 = mild waddling, lordosis, and/or toe walking; 3 = moderate waddling, lordosis, and/or toe walking; 4 = severe waddling, lordosis, and/or toe walking; 5 = walks only with assistance (ie, braces, cane, crutches); 6 = stands, but unable to walk; 7 = confined to wheelchair.
 - Stairs test is based on the subject climbing 4 stairs. It is scored as: 1 = climbs four stairs without assistance; 2 = supports one hand on thigh; 3 = supports both hands on thighs; 4 = climbs stairs in upright position but with aid of railing; 5 = climbs while clinging to the railing with both hands; 6 = climbs only a few steps; 7 = unable to climb steps.
 - Gowers' maneuver test is based on the subject lying down on the floor, then rising from the floor to get to a standing position. This is scored as: 1 = normal; 2 = butt first maneuver, one hand on floor; 3 = butt first maneuver, two hands on floor; 4 = unilateral hand support on thigh; 5 = bilateral hand support on thighs; 6 = arises only with aid of an object (table, chair, etc); 7 = unable to rise.

- Chair test is based on the subject arising from a sitting position in a chair to a standing position. This is scored as: 1 = normal; 2 = with wide base and/or difficulty but without support; 3 = with support on one thigh; 4 = with support on both thighs; 5 = with support on arms of chair or on a table; 6 = not possible.

GSGC was performed by ambulatory subjects only. The total GSGC score ranges from 4 (normal performance) to 27 (worst performance).

6. Other motor function tests – ambulatory subjects only

For each of these motor function tests, the actual time (in seconds [s]) that the subject takes to perform the test and the assigned score (which indicates the level of difficulty with which the patient performed this task) are recorded for analysis.

- Gowers' maneuver test is based on the patient lying down on the floor, then rising from the floor to get to a standing position. The time is measured in seconds (s) and assigned the test score.
- 10-meter walk test (10MWT) is based on the time it takes the subject to walk 10 meters. The score from this test is used as the Gait score in GSGC.
- 4-stair climb is based on the subject climbing 4 stairs.
- Timed Up and Go (TUG) test represents the time it takes the subject to stand up from the chair, walk to the line on the floor (about 3 meters), turn around, walk back to the chair, and sit down, all at the regular pace.

7. Rasch-built Pompe-specific Activity (R-PAct) consists of 18 questions, each scored on a scale from 0 = 'no,' 1 = 'yes, but with difficulty,' to 2 = 'yes, without difficulty.'

The 'summed raw score' or total score ranges from 0 to 36, with higher values representing lower level of disease impact on the muscles. The total score will be calculated simply by summing up the observed scores across the 18 items. The total score is analyzed as a continuous variable.

8. Rotterdam Handicap Scale (RHS): This consists of 9 questions, each scored on a scale from 1 = 'unable to perform task' to 4 = 'able to perform task independently or completely.'

The total score ranges from 9 to 36, with higher values representing lower level of handicap. The total score is obtained as the sum of the individual scores, and it will be analyzed as a continuous variable. The instrument will be scored using the traditional 50% response rule, described as follows:

If a score of '0 = not applicable' is provided, it is interpreted as a missing response or an unanswered question.

If $\geq 50\%$ of the questions were answered (ie, at least 5 out of 9 responses are available), the total score is obtained as: Total = $([\text{Sum of all available scores}] \times 9) / (9 - [\text{Number of missing items}]) = (\text{Mean of all available scores}) \times 9$ ([Merkies, Schmitz et al. 2002](#)).

Otherwise (ie, if less than or equal to 4 out of 9 questions were answered), the total score will be considered missing ('.').

9. Fatigue Severity Scale (FSS): This consists of 9 questions, each scored on a scale from 1 = ‘completely disagree’ to 7 = ‘completely agree.’

The total score ranges from 9 to 63, with higher values representing higher level of fatigue due to the disease condition. The total score is obtained as the sum of the individual scores, and it will be analyzed as a continuous variable. The 50% response rule will be applied.

If at least 5 out of 9 item responses are available, the total score will be calculated as: $\text{Total} = ([\text{Sum of all available scores}] \times 9) / (9 - [\text{Number of missing items}]) = (\text{Mean of all available scores}) \times 9$. Otherwise, the total is considered missing.

10. PROMIS® Short Forms:

- PROMIS – Physical Function Short Form 20a (v2.0) consists of 20 questions. The first 14 questions are each scored on a scale from 1 to 5 as follows: 1 = unable to do; 2 = with much difficulty; 3 = with some difficulty; 4 = with a little difficulty; 5 = without any difficulty; the next 6 questions are each scored on a scale from 1 to 5 as follows: 1 = cannot do; 2 = quite a lot; 3 = somewhat; 4 = very little; 5 = not at all.

The total score ranges from 20 – 100, with higher scores indicating more mobility.

- PROMIS – Fatigue Short Form 8a consists of 8 questions, each scored on a scale from 1 to 5 as follows: 1 = not at all; 2 = a little bit; 3 = somewhat; 4 = quite a bit; 5 = very much; and 2 questions, each scored on a scale from 1 to 5 as follows: 1 = never; 2 = rarely; 3 = sometimes; 4 = often; 5 = always.

The total score ranges from 8 – 40, with higher scores indicating more fatigue.

- PROMIS – Upper Extremity Short Form 7a consists of 7 items each scored on a decreasing scale from 1 to 5 as follows: 1 = unable to do; 2 = with much difficulty; 3 = with some difficulty; 4 = with a little difficulty; 5 = without any difficulty.

The total score ranges from 7 – 35, with higher scores indicating less disability in the upper extremity.

- PROMIS – Dyspnea Severity Short Form 10a consists of 10 questions each scored on a scale from 0 to 3 as follows: 0 = no shortness of breath; 1 = mildly short of breath; 2 = moderately short of breath; 3 = severely short of breath.

The total score ranges from 10 – 50, with higher scores indicating greater shortness of breath.

The total score of each PROMIS instrument is obtained by summing up the individual scores, and it will be analyzed as a continuous variable.

11. Global impression of change

- SGIC: The Subject’s Global Impression of Change involves 8 questions assessing each of the following functional areas:
 - overall physical wellbeing
 - effort of breathing

- muscle strength
- muscle function
- ability to move around
- activities of daily living
- energy level
- level of muscular pain

Each of the 8 functional items is scored on a 7-point rating scale as follows: 1 = very much worse; 2 = much worse; 3 = worse; 4 = no change; 5 = improved; 6 = much improved; 7 = very much improved.

For each functional item, a ternary response is defined as: “Improved” = item response of 5 or higher, ‘No change’ = item response of 4, or “Declining” = item response of 3 or lower.

- PGIC: The Physician’s Global Impression of Change (PGIC) is based on a single question that is scored on a 7-point rating scale, similarly to the SGIC.
A ternary response is created from the responses, defined as: “Improved” = response of 5 or higher, “No change” = response of 4, or “Declining” = response of 3 or lower.
